3.2 STUDY TREATMENT

The patients will be assigned to one of two treatment group in 1:1 ratio:

- Group 1. OKITASK® 40 mg – 35 patients
- Group 2. Placebo – 35 patients

The patient will assess pain by VAS at 0' – immediately before study drug dosing.

Upon study drug administration the patients will immediately start two stopwatches. One of them will be stopped once the patient feels first perceptible pain relief; the second one will be stopped once the patient feels the meaningful pain relief.

The patient will stay at the site for 6 hours post-dose for pain and AE assessment. Pain intensity will be assessed by VAS at 5', 10', 15', 30', 45', 60' (1 hour), 90' (1.5 hours), 120' (2 hours), 180' (3 hours), 240' (4 hours), 300' (5 hours), and 360' (6 hours) post-dose.

Pain relief will be assessed by VAS at 5', 10', 15', 30', 45', 60' (1 hour), 90' (1.5 hours), 120' (2 hours), 180' (3 hours), 240' (4 hours), 300' (5 hours), and 360' (6 hours) post-dose.

Patients should mark actual time points of VAS measurement. Deviations from planned time points will not be considered as protocol deviations. Only omitted values will be considered as protocol deviations.

Patients' overall assessment will be performed right before the discharge from the site.

Follow-up phone call to the patient to assess AEs will be performed on Day 3 (48 hours

after the study drug dosing). Any SAE spontaneously reported by the patient within 30 days of dosing will be collected.

Should the patient require rescue medication at any time during 6 hours post-dose, the last VAS measurement and patient's overall assessment will be performed before the rescue medication dosing.

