⁶ The time of stopwatch will be recorded on eCRF

⁷ The time of stopwatch will be recorded on eCRF

⁸ Height will be registered as reported by the patient.

⁹ In the event of poor pain control, subjects will be allowed access to rescue medication for analgesia (Paracetamol 500-1000 mg). Time to REMD (rescue) with an alternative analgesic, if it occurred, will be recorded. Subject will be encouraged to postpone the rescue medication until after 1 h post dose. If Paracetamol 500-1000 mg is not effective, the patient will be allowed to take another dose of Paracetamol 500-1000 mg every 6-8 hours; maximum daily dose is 4000 mg.

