5.2 SECONDARY OBJECTIVES

Secondary objectives of this study are to assess the following efficacy and safety parameters of OKITASK® 40 mg granules versus Placebo in patients with acute pain syndrome after removal of one molar tooth:

- Time profile of pain and time profile of pain relief using VAS scales
- Time to first perceptible pain relief (TFPR) and time to meaningful pain relief (TMPR)
- Proportion of patients requiring rescue medication and time to rescue medication
- Patient's overall assessment
- Rate of adverse events (AE)

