8.1 INTENT-TO-TREAT POPULATION

The Intent-to-treat (ITT) population will include all randomized patients who receive at

least one dose of study medication and have at least one post-baseline¹ efficacy measurement; it will be based on the treatment randomized, regardless of the treatment actually received. The ITT will be used for all efficacy analyses. Subject will be summarized according to the treatment to which they were randomized.

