10.2 SECONDARY EFFICACY

Secondary efficacy variables will be analyzed only for ITT population.

¹ Clinically significant

AUC_{0-6h} without or with LOCF of pain relief profile between time 0 (baseline value of VAS) and 6 hours post-treatment. AUC_{0-6h} analysis will be based on **actual rather than scheduled timings** and will be calculated using the trapezoidal rule (see as per primary variable).

Pain profile – Pain intensity profile will be analyzed using Analysis of Variance (ANOVA) for repeated measurements. The model will include fixed effect terms for clinical site, time point and treatment. Time point will be specified as a repeated measurement. In order to select an appropriate matrix for the observations within each subject, 3 models will be fitted using the compound symmetry, Huynh-Feldt and unstructured structures. The matrix for the final model will be selected using Akaike's Information Criterion where the lowest value indicates the best fit. The importance of the treatment-by-site interaction will be investigated but if the term is not significant at the 10% level, it will be excluded from the final model. The adjusted least squares mean will be estimated for each combination of time point and treatment. The estimated treatment difference between OKITASK® and placebo at each time point will be presented together with the corresponding 95% confidence interval. Pain profile will be analyzed based on **scheduled rather than actual timings**.

SAS code example:

```
proc mixed data=locf method=REML order=internal1;
  class patid site trt time;
  model pain = trt time trt*time
    site trt*site/ intercept ddfm=satterth;
  repeated time/ type=CS2 subject=patid(trt);
  lsmeans trt*time/ diff=all cl;
run;
```

Pain relief – Pain relief will be analyzed in the same way.

LOCF replaced data of pain intensity and pain relief will be presented graphically by treatments and time points.

Time to first perceptible relief (TFPR)³ – Kaplan-Meier curve and Log rank test will be used to describe and test treatment profile differences. In table it will be presented with median, 95% CI and p-value from Log rank test.

Time to meaningful pain relief (TMPR)⁴ – Kaplan-Meier curve and Log rank test will be used to describe and test treatment profile differences. In table it will be presented with median, 95% CI and p-value from Log rank test.

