Time to REMD – Time to rescue medication will be calculated for each subject and presented using only median value. If the number of subjects will be adequate Kaplan-Meier curve and Log rank test will be used to describe and test treatment profile differences.

Patient's overall assessment – will be described as nominal data (6 hours post-

¹ Data must be sorted!

² CS or HF or UN

³ CRF data

⁴ CRF data

dose). Mann-Whitney¹ test will be applied in order to test differences between treatments response.

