12. TABLE EXAMPLES¹

Table 12.1 Disposition

	OKITASK® N = XX	PLACEBO N = XX
Screened		xx
Safety population	xx (xx.x%)	xx (xx.x%)
Intent-to-treat (ITT) population	xx (xx.x%)	xx (xx.x%)
Per-Protocol (PP) population	xx (xx.x%)	xx (xx.x%)
Study completion	xx (xx.x%)	xx (xx.x%)
Early termination	xx (xx.x%)	xx (xx.x%)
Adverse event	xx (xx.x%)	xx (xx.x%)
Death	xx (xx.x%)	xx (xx.x%)
Patient required rescue medication	xx (xx.x%)	xx (xx.x%)
Lost to follow-up	xx (xx.x%)	xx (xx.x%)
Consent withdrawn	xx (xx.x%)	xx (xx.x%)
Investigator decision	xx (xx.x%)	xx (xx.x%)
Protocol violation, including non-compliance	xx (xx.x%)	xx (xx.x%)
Patient required prohibited medications		
Protocol entry criteria not met	xx (xx.x%)	xx (xx.x%)
The patient starts of another study drug	xx (xx.x%)	xx (xx.x%)
Study is stopped by Sponsor decision	xx (xx.x%)	xx (xx.x%)
Study is stopped by regulatory instance / ethics committee	xx (xx.x%)	xx (xx.x%)
Pregnancy	xx (xx.x%)	xx (xx.x%)
Other	xx (xx.x%)	xx (xx.x%)

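### Time to rescue medication: only a median is unconditional, the Kaplan-Meier and log-rank analysis depends on an undefined number of subjects, and the median has no stated denominator

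*SAP*

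**What the plan says.** Section 5.2 lists as a secondary objective: "Proportion of patients requiring rescue medication and time to rescue medication".

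Section 10.2 (Time to REMD) gives the analysis in two sentences. The first is "Time to rescue medication will be calculated for each subject and presented using only median value". The second is conditional: "If the number of subjects will be adequate Kaplan-Meier curve and Log rank test will be used to describe and test treatment profile differences". No number is attached to the condition, and the text does not say whether it refers to patients or to rescue events.

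For the two relief endpoints, TFPR and TMPR, the same section plans the Kaplan-Meier curve and log-rank test without any condition: "In table it will be presented with median, 95% CI and p-value from Log rank test".

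On who has a time, Table 3.1 note 9 (section 3.3) says: "Time to REMD (rescue) with an alternative analgesic, if it occurred, will be recorded". Section 8.1 says: "The ITT will be used for all efficacy analyses". Section 3.2 places rescue within the 6-hour stay on site. No section says what happens to a patient who is never rescued.

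The Table 12.18 shell, headed ITT, has a median, a 95% CI for the median (footnoted as depending on the data) and a log-rank p-value row. The first footnote of section 12 says that reported tables may differ from the examples. Table 12.1 counts, by arm, the termination reason "Patient required rescue medication".

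**The concern.** Two things are left open for an endpoint that is named in the objectives.

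**Whether to test.** The group size is planned at 35 per arm, so the number likely to be in doubt is the number of rescues, which is known only from the trial data. Without a threshold, the choice between a bare median and a full time-to-event comparison can be made once the result is visible.

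**What the median is.** A time is to be calculated for every subject but exists only for those rescued. The reported figure could be a Kaplan-Meier median in all ITT patients or a simple median among rescued patients. These answer different questions. The second also conditions on an outcome that treatment is meant to change. A reader of the report could not tell from the SAP which was planned.

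At stake is whether the one guaranteed summary can show a treatment difference at all.

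**Working it through.** **Group size.** The SAP states no figure for time to rescue, so there is none to reproduce. The only input it supplies is 35 per arm, from the AUC calculation in section 6: 2 × (1.960 + 0.842)² × 121² / 90² = 28.4, so 29 per arm; 29 / 0.85 = 34.1, so 35.

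**Assumptions.** The rescue rates are assumed because the SAP gives none. F is the proportion rescued by 6 h, with a constant hazard over 6 h and no earlier censoring.

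**Formulas.**
- Hazard: h = −ln(1 − F) / 6.
- Median among rescued patients only: −ln(1 − F/2) / h.
- Kaplan-Meier median: ln 2 / h, which lies beyond 6 h for any F below 0.5.
- Expected events: 35 × (F placebo + F active).
- Both Kaplan-Meier medians not reached: at most 17 of 35 rescued in each arm.
- Log-rank power: simulation, 10,000 trials per scenario, two-sided 0.05.

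**Worked case, 40% placebo v 10% active.** The hazards are 0.5108/6 = 0.0851 and 0.1054/6 = 0.0176 per hour, so the hazard ratio is 0.5108/0.1054 = 4.85. The rescued-only medians are 0.2231/0.0851 = 2.62 h and 0.0513/0.0176 = 2.92 h. The active-arm median would rest on about 35 × 0.10 = 3.5 patients.

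| Placebo / active rescued | Expected events | Hazard ratio | Rescued-only medians (h) | Both Kaplan-Meier medians not reached | Log-rank power |
|---|---|---|---|---|---|
| 20% / 10% | 10.5 | 2.1 | 2.8 v 2.9 | nearly all trials | 21% |
| 30% / 15% | 15.75 | 2.2 | 2.7 v 2.9 | over 99% | 32% |
| 30% / 10% | 14 | 3.4 | 2.7 v 2.9 | over 99% | 58% |
| 30% / 5% | 12.25 | 7.0 | 2.7 v 3.0 | over 99% | 83% |
| 40% / 20% | 21 | 2.3 | 2.6 v 2.8 | 89% | 45% |
| 40% / 10% | 17.5 | 4.8 | 2.6 v 2.9 | 89% | 86% |
| 60% / 20% | 28 | 4.1 | 2.3 v 2.8 | 11% | 95% |

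**Higher rescue rates.** At 60%/40% both medians are not reached in about 10% of trials, and at 70%/40% in under 1%. At 80%/60% the Kaplan-Meier medians are 2.6 v 4.5 h, a clear contrast.

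**Validity with few events.** With no treatment effect, the log-rank test rejects in 5.3%, 5.0%, 4.8% and 4.9% of simulated trials at 7, 10.5, 14 and 21 expected events. Few events cost power; they do not invalidate the test.

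**Proportion rescued.** By the Newcombe method, 14/35 v 4/35 gives a difference of 28.6 points (95% CI 8.1 to 46.4), and 10/35 v 5/35 gives 14.3 points (−5.1 to 32.6). This contrast stays readable where the median does not.

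**The case against.** **The shell already shows the test.** Table 12.18 has a log-rank row, and its data-dependent footnote sits on the CI heading, not on the p-value. A reader might infer from section 10.2 that no comparison of time to rescue is planned; that goes too far. But a shell that may change does not override a condition in the text. What stands is that text and shell disagree.

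**Kaplan-Meier implies censoring.** If the method is used, never-rescued patients would by convention be censored at the end of the 6-hour stay, and the ITT heading of Table 12.18 favours that reading. This narrows the gap but does not close it: the median-only fallback carries no such convention.

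**TFPR and TMPR are not a clean contrast.** They lack the condition, but section 10.2 states no censoring rule for them either. Only the undefined condition is peculiar to rescue.

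**The illustrations assume low rescue.** This is correct. One might infer that the median is bound to be uninformative. The SAP neither gives nor excludes rates above one half, and at such rates the Kaplan-Meier median can work.

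**The proportion is already tabulated.** Table 12.1 gives number and percent by arm, and section 11.1 makes frequencies the default for nominal data. The missing interval for the difference is therefore not an error; adding one is an improvement.

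**Low power justifies caution.** With few events the test may well miss a real effect. That is a reason to interpret it carefully, not to leave its use undecided.

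**Conclusion.** The point holds in limited form. Section 10.2 makes a median the only unconditional summary of time to rescue. It leaves the curve and the test to an undefined judgement that can follow sight of the data, and it gives the fallback median no denominator. It also disagrees with the Table 12.18 shell.

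The size depends on rescue rates that the SAP does not give. Under a constant hazard with 35 per arm and both rates at 40% or below, the Kaplan-Meier median is not reached in either arm in 89% or more of trials. A rescued-only median then differs by about 0.1 to 0.3 h even for hazard ratios from 2 to 7. At higher rates the Kaplan-Meier median becomes useful, while the rescued-only median remains weak (2.3 v 2.8 h at 60%/20%).

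The endpoint is secondary. The primary AUC test and the sample size are not affected. The change should be made, but it does not threaten the trial's main conclusion.

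**What to change.** Replace the two Time to REMD sentences in section 10.2 with:

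> Time to rescue is measured from study drug dosing and analysed by Kaplan-Meier and log-rank in all ITT patients regardless of the number of events. Patients not rescued are censored at 6 h, or at the last observation if earlier. Medians not reached are reported as such.

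This brings the text into line with Table 12.18. Naming dosing as the origin also removes any doubt raised by section 11.2, which counts time periods from the informed consent date. A censoring rule for TFPR and TMPR could be added in the same edit.

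Optional, because the proportion rescued is part of a secondary objective: add to Table 12.18 the number and percent rescued within 6 h per arm, with a 95% CI for the difference.

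The cost is a few sentences and at most one table row; time to rescue is already to be recorded. The downside is low log-rank power with few events, about 21% to 32% in the 20%/10% and 30%/15% scenarios. A non-significant result must not be read as no effect.

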3.3 FOLLOW-UP

Follow-up phone call to the patient to assess AEs will be performed on Day 3±1 (48 hours after the study drug dosing). Any SAE spontaneously reported by the patient within 30 days of dosing will be collected.

The study procedures schedule is summarized in Table 3.1.

Table 3.1 Schedule of visits and procedures

Test/Examination	Screening	Study treatments													ED ¹	Follow-up
		Time (Post-dose)														
Day	Day-4...Day 1	Day 1													Day 1	Day 3±1
		0.08	0.17	0.25	0.5	0.75	1	1.5	2	3	4	5	6	>1	48	
		5	10	15	30	45	60	90	120	180	240	300	360	>60		
Informed consent & screening n° assignment		X														
Demography		X														
Medical history and underlying disease		X														
Oral cavity examination		X														
Height		X														
Weight		X														
Vital signs		X														
Pregnancy test		X														
Extraction of a molar tooth	X (Day 1)															
Pain Intensity Assessment VAS (0-100 mm) ³	X	X														
Inclusion/exclusion criteria ⁴	X															
Randomization number assignment			X													
Patient's overall assessment (5-point scale) ⁵				X											X	X
Pain Relief Assessment VAS (0-100 mm)																
Time to first perceptible relief (TFPR) measured by stopwatch ⁶														X		
Time to meaningful pain relief (TMRP) measured by stopwatch ⁷														X		
Rescue medication (if applicable) ⁸															X ⁹	
Concomitant medications	X	X													X	X
Previous therapy(ies)	X	X														
Adverse events	X	X												X	X	

¹ Should the patient require rescue medication at any time during 6 hours post-dose, the last VAS measurement and patient's overall assessment will be performed before the rescue medication dosing. Subjects will be encouraged to postpone the rescue medication until after 1-hour post-dose. The ED assessments will be performed before rescue treatment; actual time of VAS will be captured.

² After surgery, before the study drug administration

³ Patients should mark actual time points of VAS measurement. Deviations from planned time points will not be considered as protocol deviations. Only omitted values will be considered as protocol deviations.

⁴ Confirmation of the Inclusion/Exclusion criteria prior to randomization

⁵ Patients should mark actual time points of VAS measurement. Deviations from planned time points will not be considered as protocol deviations. Only omitted values will be considered as protocol deviations.

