OKITASK [®]	5 minutes	xx	xx.x (xx.x)	xx.x	xx.x	xx.x	xx.x
PLACEBO	5 minutes	xx	xx.x (xx.x)	xx.x	xx.x	xx.x	xx.x
$\mu_T - \mu_R$	95% CI		xx.x [xx.x; xx.x]				
...							
OKITASK [®]	6 hours	xx	xx.x (xx.x)	xx.x	xx.x	xx.x	xx.x
PLACEBO	6 hours	xx	xx.x (xx.x)	xx.x	xx.x	xx.x	xx.x
$\mu_T - \mu_R$	95% CI		xx.x [xx.x; xx.x]				

Figure 12.3 Secondary efficacy. Visual Analogue Scale. Pain Relief profile. ITT population. N = XX

Similar to Figure 12.1

Figure 12.4 Secondary efficacy. Visual Analogue Scale. Difference in Pain Relief means with 95% CI. ITT population. N = XX

Similar to Figure 12.2

Table 12.17 Time to first perceptible relief (TFPR) and Time to meaningful pain relief (TMRP). ITT population. N = XX

Parameter Treatment	Median	95% CI
Time to first perceptible relief (TFPR) hours		
OKITASK®	xx.x	[xx.x; xx.x]
PLACEBO	xx.x	[xx.x; xx.x]
Log rank test p-value	0.0000	
Time to meaningful pain relief (TMRP) hours		
OKITASK®	xx.x	[xx.x; xx.x]
PLACEBO	xx.x	[xx.x; xx.x]
Log rank test p-value	0.0000	

Table 12.18 Time to rescue medication (REMD). ITT population. N = XX

Parameter Treatment	Median	Median 95% CI ¹
Time to rescue medication (REMD) hours		
OKITASK®	xx.x	xx.x [xx.x; xx.x]
PLACEBO	xx.x	xx.x [xx.x; xx.x]
Log rank test p-value	0.0000	

Table 12.19 Overall assessment 6-hours post-dose. ITT population. N = XX

	OKITASK® N = XX	PLACEBO N = XX
(1) Very good	xx (xx.x%)	xx (xx.x%)
(2) Good	xx (xx.x%)	xx (xx.x%)
(3) Satisfactory	xx (xx.x%)	xx (xx.x%)
(4) Poor	xx (xx.x%)	xx (xx.x%)
(5) Very poor	xx (xx.x%)	xx (xx.x%)
No data ²	xx (xx.x%)	xx (xx.x%)
p-CMH		0.0000

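### The overall assessment is analysed at 6 hours only, and no rule says how the rating that rescued patients give before rescue enters that analysis

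*SAP*

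**What the plan says.** **Analysis.** SAP Section 10.2 states that the overall assessment "will be described as nominal data (6 hours post"-dose), and that a "Mann-Whitney¹ test will be applied in order to test differences between treatments response". A footnote implements the test as the PROC FREQ CMH row-mean-score statistic. The output shell is headed "Overall assessment 6-hours post-dose. ITT population"; it has five categories from very good to very poor, plus a No data row.

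**Collection.** Section 3.2 gives two occasions after dosing. In general, "Patients' overall assessment will be performed right before the discharge from the site", and patients stay 6 hours. For a patient who needs rescue within those 6 hours, "the last VAS measurement and patient's overall assessment will be performed before the rescue medication dosing". Footnote 1 to Table 3.1 treats the second occasion as early discontinuation (ED): "The ED assessments will be performed before rescue treatment; actual time of VAS will be captured". Table 12.1 lists need for rescue among the reasons for early termination.

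**Missing data.** Section 7.1 names primary and secondary variables when it introduces LOCF, but the replacement rule it then writes is for pain scores.

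**The concern.** The time label in Section 10.2 selects which rating is analysed, and for a rescued patient the only rating provided for after dosing does not carry that label. A programmer working from the text would find no 6-hour record for that patient, count the patient under No data and pass nothing to the test. Remaining in the ITT population does not help a patient who has no analysed value.

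The missing value would then be caused by the outcome: patients lose their rating because pain control was poor. The test would compare only patients who managed without rescue, a subset defined after randomisation and possibly of different size in each arm. The SAP provides for collecting the ratings of the excluded patients, so the loss is avoidable. An unwritten choice between two data sets also leaves room for it to be made once results are known.

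**Working it through.** **1. Is there a linking rule?** Section 10.2 and Table 12.19 say 6 hours. Section 3.2 and footnote 1 to Table 3.1 place a rescued patient's rating before rescue, as an ED assessment. Section 7.1 could have joined the two, but its rule covers pain scores. Its nearest analogue, the last case of Table 7.1, leaves values missing to the end of observation unreplaced and calls the AUC invalid. No linking rule exists.

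**2. Plan figure.** The SAP states no effect, rescue rate or power for this endpoint. Only the arm size is taken from it: Section 6 needs 29 per group with 15% drop-out, and 29/0.85 = 34.1, rounded up to 35.

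**3. Assumptions (not from the SAP).** Ratings run from 1 = very good to 5 = very poor.
- Not rescued, placebo: 0.10/0.30/0.35/0.20/0.05, mean 2.80
- Not rescued, active: 0.15/0.40/0.30/0.12/0.03, mean 2.48
- Rescued, either arm: 0/0/0.15/0.50/0.35, mean 3(0.15) + 4(0.50) + 5(0.35) = 4.20

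**4. Mean difference, placebo minus active.** With 6-hour ratings only it is 2.80 − 2.48 = 0.32, whatever the rescue rates rP (placebo) and rA (active). With all ratings, each arm's mean is (1 − r) × (mean of those not rescued) + r × 4.20, so the difference is

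0.32 + 1.40 rP − 1.72 rA.

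For 40% and 15%: 0.32 + 0.560 − 0.258 = 0.62. The placebo mean is 0.6 × 2.80 + 0.4 × 4.20 = 3.36 with all ratings, against 2.80 with 6-hour ratings only.

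**5. Power.** Mann-Whitney test at two-sided 0.05, 35 per arm, 2000 simulated trials per row.

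| Rescue, placebo/active | Expected N with a 6 h rating | Difference, 6 h only | Difference, all | Power, 6 h only | Power, all |
|---|---|---|---|---|---|
| 20%/10% | 28/31.5 | 0.32 | 0.43 | 21% | 35% |
| 40%/15% | 21/29.75 | 0.32 | 0.62 | 21% | 62% |
| 60%/30% | 14/24.5 | 0.32 | 0.64 | 15% | 62% |
| 20%/20% | 28/28 | 0.32 | 0.26 | 22% | 17% |
| 30%/40% | 24.5/21 | 0.32 | 0.05 | 19% | 5% |

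**6. Where the direction turns.** The two differences agree when 1.40 rP = 1.72 rA, that is rP/rA = 1.23. Above that ratio the 6-hour-only analysis dilutes the difference; below it, it inflates the difference. If patients not rescued rate the two arms alike (both 2.80), the 6-hour-only difference is 0 and the all-ratings difference is 1.40(rP − rA). At 40%/15% that is 0.35, with power 5% against 25%: an effect acting wholly through rescue is not seen. With equal rescue rates there is then no distortion.

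**7. Test coding.** The row-mean-score statistic equals Mann-Whitney only with rank scores; the PROC FREQ default uses the category numbers. In simulation the two fell on different sides of p = 0.05 in about 3% of trials.

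**The case against.** The SAP nowhere says that rescued patients are excluded. Section 3.1 also records an overall assessment before randomisation, so the 6-hour label may serve only to separate the final rating from that one. Section 8.1 keeps rescued patients with a post-baseline measurement in ITT for all efficacy analyses, and the No data row is footnoted as applying only if needed. Even the absence of a 6-hour rating in a rescued patient is inferred, from the ED wording and Table 12.1. All this stands. It makes exclusion the literal reading, not a stated rule. It does not supply the missing rule.

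A reader might go further and infer that the plan drops treatment failures and so makes placebo look better at the drug's expense. The documents do not support that. Exclusion flatters both arms, and dilution needs clearly more rescue on placebo, which is plausible but not stated.

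The figures also depend on the model. When the rating was driven by change in pain plus noise under the planning AUC effect, the loss was small at low rescue (0.78–0.80 with all ratings against 0.74 at 19%/10%) and larger at 48%/26% (0.61).

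Finally, rescued patients stay visible in Tables 12.1 and 12.18. That limits the harm but does not repair this comparison.

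**Conclusion.** The concern holds as a badly fixed time point with no linking rule. Read literally, Section 10.2 and Table 12.19 confine the test to patients who did not need rescue, although the plan has the others rated before rescue. Provided that rescued patients rate treatment worse, both arms are flattered and the difference is biased in a direction that depends on the rescue rates: towards no difference if placebo is rescued clearly more often, and towards the drug if rescue is equal or higher on active and patients not rescued rate active better.

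The direction cannot be settled from the SAP, and the power figures illustrate assumed rates and rating distributions only. The endpoint is secondary and was not used for sample size; the primary analysis is not affected by this point. It should be corrected before unblinding. The score option is a minor programming note.

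**What to change.** - **Section 10.2:** define the analysed value for every ITT patient as the 6-hour rating or, if the patient was rescued or discontinued earlier, the rating recorded before rescue or at ED. This also settles which rating counts if a rescued patient is rated again at discharge.
- **Table 12.19:** retitle it to match, keep the No data row for patients with no post-dose rating, and show the number of ED ratings in each arm.
- **Sensitivity:** report the 6-hour-only analysis alongside, labelled as restricted to patients observed to 6 hours.
- **Test footnote:** specify SCORES=RANK, so that the PROC FREQ statistic is the Mann-Whitney test named in the text.

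The cost is a few lines of SAP text, one changed table shell, one extra output and one program option. The schedule already collects the ratings, so no new data are needed.

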3.1 SCREENING

At Screening after signing the informed consent form, patient's demography, medical history and concomitant medications will be collected, oral cavity will be examined, weight and vital signs will be measured and pregnancy test will be performed for inclusion/exclusion criteria assessment. Screening procedures might take up to 4 days before the scheduled tooth extraction procedure including the actual day of extraction.

On Day 1 the patient will undergo extraction of a molar tooth as indicated for the patient's dental condition. The tooth extraction will be conducted using routine technics and anesthetics (recommended types of anesthesia are provided in section 5.9 Concomitant and rescue therapy of the protocol). After that the patient will stay at the site for treatment of pain syndrome according to the protocol.

Pain intensity will be assessed using VAS within 3 hours after the tooth extraction procedure. Patient's overall assessment will be also recorded. If pain intensity on VAS is above 30 mm and pain relief is required, the patient will be randomized in the study.

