11.2 OTHER

Calculation of time periods will be done relative to the date of the informed consent (IC).

¹ Proc Freq, CMH test, row-mean score difference

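### The overall assessment is rated before dosing, but its between-arm test leaves that rating out; adjusting for it is a cheap gain in precision if the two ratings correlate

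*SAP*

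**What the plan says.** Collection of the rating:

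- Section 3.1, on the period after the extraction when the qualifying VAS is taken: "Patient's overall assessment will be also recorded". Randomisation follows, so by design each randomised patient has a pre-dose rating.
- Table 3.1 carries a single row for the item, "Patient's overall assessment (5-point scale".
- Section 3.2 repeats it after dosing: "Patients' overall assessment will be performed right before the discharge from the site". For patients who need rescue, "the last VAS measurement and patient's overall assessment will be performed before the rescue medication dosing".

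Analysis of the rating:

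- Section 10.2 describes the 6-hour rating and says that a Mann-Whitney "test will be applied in order to test differences between treatments response". The footnote gives the implementation: "Proc Freq, CMH test, row-mean score difference". No covariate or stratum is named.
- Table 12.19 is titled "Overall assessment 6-hours post-dose" and shows the five categories by arm at that occasion only.
- The baseline list in section 9.2 does not include the pre-dose rating.
- The clause in section 10.1 that lets covariates enter a model concerns the ANOVA of the AUC. Section 10.2 does not extend it to the overall assessment.

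**The concern.** The plan schedules a baseline value of a named secondary endpoint and then names no use for it. When a baseline value predicts the outcome, leaving it out keeps patient-to-patient variation in the comparison that could have been removed. With 35 patients per arm, a real difference in the overall assessment is then somewhat more likely to be missed. The data are already planned, so the question is whether the improvement is worth a few lines in section 10.2.

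**Working it through.** **Inputs.** 35 per arm enrolled, 29 per arm evaluable, alpha 0.05 (section 6). Five categories (Table 12.19). The SAP gives neither a power figure for this endpoint nor a correlation between the two ratings. The 80% starting power and every rho below are therefore assumptions.

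**The plan's own figure.** Section 6 sizes the trial for the AUC: n = 2 × (1.960 + 0.842)² × 121² / 90² = 28.4, so 29 per arm. For drop-out, 58 / 0.85 = 68.2, so 69, which the plan rounds to 70. The stated size reproduces. It fixes the 35 per arm but says nothing about the overall assessment.

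**Closed-form guide.** Adjusting for a baseline that correlates rho with the outcome multiplies the variance by 1 − rho². A comparison with 80% power then has power Φ(2.802 / √(1 − rho²) − 1.960):

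| rho between the ratings as analysed | variance factor | adjusted power | unadjusted n per arm equivalent to 35 adjusted |
|---|---|---|---|
| 0.2 | 0.96 | 81.6% | 36.5 |
| 0.3 | 0.91 | 83.6% | 38.5 |
| 0.5 | 0.75 | 89.9% | 46.7 |

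**Simulation on the 5-point scale.** Latent bivariate normal ratings were cut into five categories, with 35 per arm and a latent shift of 0.72 chosen to give about 80% unadjusted power (6,000 replicates per setting). The unadjusted test uses pooled ranks of the post-dose rating, which makes the CMH test the Mann-Whitney test. The adjusted test takes residuals e of the post-dose ranks from a straight-line fit on the pre-dose ranks. It then uses Z = T / √V, where T is the sum of e in one arm and V = [N² / (2N − 1)] × mean(e²), with N = 35. The Monte Carlo standard error of each power is √(0.8 × 0.2 / 6,000), about 0.5 points.

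| latent rho | pre-dose categories | unadjusted | adjusted | gain (points) |
|---|---|---|---|---|
| 0 | five | 79.6% | 79.1% | −0.5 |
| 0.2 | five | 80.7% | 81.2% | 0.5 |
| 0.3 | five | 80.5% | 82.9% | 2.4 |
| 0.5 | five | 80.0% | 87.7% | 7.7 |
| 0.5 | three | 79.8% | 86.8% | 7.0 |
| 0.2 | two, 80/20 | 80% | 80% | 0 |
| 0.3 | two, 80/20 | 79% | 80% | 1 |
| 0.5 | two, 80/20 | 80% | 84% | 4 |
| 0.3 | two, 90/10 | 80% | 80% | 0 |
| 0.5 | two, 90/10 | 79% | 82% | 3 |

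A run of 4,000 replicates gave 82% against 83% at rho 0.3, so the gain there is best read as 1 to 2 points. With no treatment effect, both tests rejected in about 4% to 5.5% of replicates.

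**Why the two tables differ.** Rho in the simulation is latent, and cutting into categories weakens it. In a further run with no treatment effect, latent 0.4 and 0.6 gave observed rank correlations of 0.355 and 0.536. Latent 0.5 therefore lies near (0.355 + 0.536) / 2 = 0.45. Putting 0.45 into the closed form gives Φ(2.802 / √0.7975 − 1.960) = 88%, in line with the simulated 87.7%.

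**The case against.** The strongest reply is that nothing in the plan is wrong. An unadjusted rank test of a randomised endpoint is a legitimate choice, no two sections conflict, and preferring a covariate-adjusted test is a matter of efficiency. That stands, and it limits the point to an improvement.

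Several stronger readings are tempting but not supported:

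- *A reader might infer that chance imbalance in the pre-dose rating biases the comparison.* It does not. Randomisation makes such imbalance part of the test's null distribution, and the simulated error rates stay near 5%.
- *A reader might infer that precision is certainly lost.* That depends on a correlation the SAP does not give. Patients are randomised only with VAS of about 30 mm or more and a need for pain relief, so their pre-dose ratings may cluster. The two-category rows show how far that shrinks the gain.
- *A reader might take the two ratings to be on the same scale as a fact.* This rests on one schedule row, and the table is broken in the text at hand. The wording of the pre-dose item is not given. If the post-dose item rates the treatment rather than the patient's state, the correlation could be low.
- *A reader might infer that the pre-dose rating will be reported nowhere.* Section 11.1 promises counts and percentages for all nominal and ordered data by arm and, for example, by visit. The table footnote in section 12 calls the shells examples. The rating is absent from the section 9.2 list and from Table 12.19, but the general rule arguably covers it.

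**Conclusion.** The point holds as a minor, low-cost improvement to one secondary analysis. The planned test is valid. It forgoes a baseline value that the trial already collects, and this costs precision only if that value predicts the post-dose rating.

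At 35 per arm and about 80% unadjusted power, adjustment gains about nil up to a latent correlation of 0.2, about 1 to 2 points at 0.3 and about 4 to 8 points at 0.5. Four points corresponds to an 80/20 split over two pre-dose categories; a 90/10 split gives about 3. The possible loss at zero correlation is under about 1 point, so the balance favours adjusting. These sizes rest on the assumed correlations, the assumed starting power and a latent normal model. The facts about what is collected and what is tested come directly from the SAP.

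**What to change.** In section 10.2, before unblinding, prespecify the test of the overall assessment as adjusted for the pre-dose rating. A rank analysis of covariance stays within the procedure already named: rank both ratings over all patients, regress the post-dose ranks on the pre-dose ranks, and apply the CMH row-mean-score test to the residuals. Name this as the deciding test for the endpoint and keep the unadjusted test as supportive. Show the pre-dose rating by arm next to Table 12.19. Confirm beforehand, from the case report form, that the pre-dose item uses the same 5-point scale.

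The cost is SAP wording, a few lines of SAS and one table block, with no new data. There are two small drawbacks. The residual-rank test gives no effect that can be read directly on the five categories, so the category counts must still be shown. A missing pre-dose rating needs a stated fill-in, such as the median pooled over both arms.
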